5.1.2 Baseline (Day 0)

Prior to randomization, potential subjects will undergo the following Baseline procedures and assessments:

- Updated medical history
- Targeted physical examination
- Vital signs
- Weight
- 12-lead ECG

- Urine pregnancy test (for FOCP)
- Updated prior and concomitant medications
- AEs that have occurred since signing informed consent

If potential subjects continue to satisfy the eligibility criteria based upon the procedures and assessments stated above, those data will become part of the Baseline visit. Those potential subjects may then be randomized and officially become subjects in the study. Subjects will again be instructed to avoid any use of the prohibited medications listed in Section 4.6 for the entire duration of the study, or until formally instructed otherwise.

Prior to dosing, the following additional Baseline procedures and assessments will be conducted at the investigational site. The Baseline central laboratory data will not be used to determine eligibility in the study as the newly enrolled subject has already been randomized. The additional pre-dose Baseline procedures include:

- Serum chemistry panel
- Lipid panel
- Hematology with differential
- Coagulation panel
- HOMA-IR

- Serum pregnancy test (for FOCP)
- Pro-C3
- ELF test
- Bile acid panel

Following the successful completion of all Baseline procedures, the subject will self-administer the first dose of the study drug, consisting of 4 tablets (1 pouch), under the supervision of investigational site staff. A 2-week supply of study drug will be dispensed to the subject to take home, and the dosing instructions and schedule will be provided (see Section 4.2). Subjects will be instructed to contact the investigational site immediately if any problems or concerns arise.

5.1.3 Double-Blind Treatment Period (Weeks 2, 6, 10, 14, 18)

During the Double-Blind Treatment Period, the following procedures and assessments will be conducted during the visits to the investigational site on:

Week 2 -

- Weight
- Serum chemistry panel

- AE monitoring
- Concomitant medications

Weeks 6 and 14 -

- Targeted physical examination
- Vital signs
- Weight
- 12-lead ECG

- Serum chemistry panel
- AE monitoring
- Concomitant medications

Week 10 -

- Weight
- Serum chemistry panel
- Lipid panel
- Hematology with differential
- Coagulation panel

- HbA1c
- Bile acid panel
- AE monitoring
- Concomitant medications

Week 18 -

- Comprehensive physical examination
- Vital signs
- Weight
- 12-lead ECG
- Serum chemistry panel
- Lipid panel
- Hematology with differential
- Coagulation panel
- HbA1c

- HOMA-IR
- Serum pregnancy test (for FOCP)
- MRI-PDFF
- Pro-C3
- ELF test
- Bile acid panel
- AE monitoring
- Concomitant medications

Note: The serum chemistry panel performed at the Week 2, Week 6, and Week 14 visits only includes testing of alkaline phosphatase (ALP), ALT, AST, gamma-glutamyl transferase (GGT), total bilirubin, direct bilirubin, and fasting glucose. The Week 10 and Week 18 bile acid panel applies only to subjects who have had the Baseline bile acid panel performed. Refer to Table 1 and Table 2 for the clinical laboratory collection schedule and corresponding analytes, respectively.

At the completion of the Weeks 2, 6, 10 and 14 clinic visits, the next 4-week supply of study drug will be dispensed to the subject. At all visits, used and unused study drug pouches will be collected from the subject; compliance with taking the study drug will be assessed.

Prior and concomitant medications will be reviewed and any changes will be recorded on the appropriate eCRF page. Generally, any new medications that are being taken are, by default, to be considered as being necessitated by an AE. Rarely, a previously unmentioned prior medication may be disclosed, and that eCRF page should be updated.

The subject is to be queried for any changes to existing AEs or any additional AEs that may have occurred during the intervening period.

5.1.4 Study Discharge

Following the successful completion of all procedures at the Week 18 visit of the Double-Blind Treatment Period, all subjects are to undergo study discharge procedures. This will include instructions to the subject to contact the investigational site immediately if any problems or concerns arise during the next 30 days of follow-up (see Section 5.1.6).

5.1.5 Early Termination

Should a subject permanently discontinue taking his/her assigned study drug, an Early Termination (ET) visit should be performed. The ET visit procedures and assessments are the same as those performed at the Week 18 visit (see Section 5.1.3). If the ET visit coincides with a regularly scheduled study visit, the ET visit procedures and assessments will be performed in its place. The subject will then be instructed to contact the investigational site immediately if any problems or concerns arise during the next 30 days of follow-up (see Section 5.1.6).

5.1.6 Follow-up Period

All subjects will undergo follow-up evaluations at least 30 days after the last dose of study drug. The follow-up can be via telephone, provided that the subject has no health concerns related to the study. The subject may be asked to return to the investigational site if the Investigator thinks it is advisable for safety reasons. The following assessments will be conducted by telephone (or other) contact:

- AE monitoring
- Concomitant medications (query for any possible relationship to an AE)

Following the completion of the follow-up procedures, the subject is officially discharged from the study.

6.0 CONDUCT OF STUDY PROCEDURES AND ASSESSMENTS

For all study procedures and assessments described in this section, refer to the Schedule of Time and Events (Table 1) and Section 5.0.

6.1 ADMINISTRATIVE PROCEDURES

6.1.1 Demographics and Medical History

The Investigator or qualified designee will obtain demographic data, medical history, and medication history for each potential subject at Screening. Demographic data will include, at a minimum, the subject's age and/or date of birth, sex, race, and ethnicity. Medical and medication history will include relevant medical conditions and treatments, including surgical procedures, within the last 10 years of Screening that the Investigator considers clinically significant.

6.1.2 Randomization and Study Drug Management

Upon confirmation of subject eligibility at the Baseline visit (see Section 5.1.2), investigational site staff will login to the designated automated system to randomize the subject and to dispense the assigned study drug kits. The designated automated system will also be used throughout the study to enter study visit data, update the subject's study disposition, and for study drug supply management. Refer to the SPM or applicable instructions for further system and process related details.

6.1.3 Subject Reminder Cards

Subject reminder cards will be provided to all (potential) subjects at each study visit. The reminder cards will inform the subject of the date and time of his/her next scheduled visit and will include any necessary instructions.

6.2 EFFICACY ASSESSMENTS

6.2.1 Magnetic Resonance Imaging

Magnetic resonance imaging-estimated proton density fat fraction will be utilized as the primary efficacy measure to quantify LFC. Proton density fat-fraction, which is a fundamental property of tissue that measures hepatic fat concentration based on the

density of mobile protons from fat (triglycerides) compared to the total density of protons from mobile triglycerides and mobile water, is well-accepted as a standardized non-invasive biomarker of LFC (Reeder et al., 2012).

Corrected T1 (or iron-corrected T1) is an MRI-based technique that characterizes tissue *in vivo* based on the fluidity of water protons within the tissue. Relative to liver tissue, the T1 measurement of free water increases with inflammation and fibrosis, but must be corrected due to the confounding effect of iron (Banerjee et al., 2014). While cT1 will not be utilized as an efficacy measure for this study, it will be utilized as a biomarker of fibrosis to qualify potential subjects given its reported correlation with histological parameters of liver disease (Pavlides et al., 2016).

Investigational sites will utilize their local MRI facility, which will be qualified according to a study-specific image acquisition protocol, to acquire the MRI-PDFF and cT1 scans. Magnetic resonance imaging scans will be performed on the subjects' abdominal region and will last approximately 10 minutes. Scan data will then be transmitted electronically via a secure portal to a central imaging laboratory for analysis. Central imaging specialists blinded to the clinical data will use the *Liver*MultiScan *Discover*TM (LMSD; Perspectum Diagnostics, Oxford, United Kingdom) investigational device to analyze the scans and report the MRI-PDFF, cT1, and T2* results to the investigational sites. The MRI-PDFF, cT1, and T2* results will be reported at Screening, with MRI-PDFF and cT1 as part of the eligibility criteria. At a minimum, clinical metrics for the MRI-PDFF will be reported at the Week 18 or ET visit. Technical and analysis specifications and procedures, including the blinded reporting of any results, will be detailed in the central imaging manual, imaging charter, and/or SPM.

6.2.2 Efficacy Related Laboratory and Biomarker Assessments

A central laboratory will be utilized to perform efficacy related clinical laboratory and biomarker assessments as specified in Table 1 and Table 2 and as described in this section. Samples for laboratory and biomarker assessments performed at Baseline must be collected **prior to study drug dosing**. The Investigator or qualified designee must review the results of all central laboratory testing to assess subject eligibility at Screening and Baseline, as well as continued study participation for the duration of the Double-Blind Treatment Period. Procedures for sample collection and handling,

including the blinded reporting of any results, will be detailed in the central laboratory manual and/or SPM.

The following laboratory and biomarker assessments will be utilized as secondary efficacy measures:

Fasting glucose, HbA1c, HOMA-IR, serum triglycerides, LDL-c, and HDL-c will be utilized in this study to assess glucose metabolism, insulin resistance, and lipid metabolism. These measures are routinely performed in the management of metabolic abnormalities that underlie the pathogenesis of NAFLD, including dyslipidemia and T2DM, the latter of which is recognized as a risk factor for progressive hepatic fibrosis (Adams and Angulo 2006).

Aspartate aminotransferase and ALT are liver-associated enzymes that will be utilized in this study to assess liver biochemistry. These enzymes are markers of liver injury that may be useful surrogate measures of NAFLD and NASH, particularly in T2DM patients (Sanyal et al., 2015).

Pro-C3 and the ELF score are biomarkers that will be utilized in this study to assess liver inflammation and fibrosis. Pro-C3 is a neo-epitope of PIIINP, which has been reported to reflect the true formation of collagen and to potentially be an accurate biomarker for the formation of fibrotic tissue in the liver (Nielsen et al., 2013). The ELF score is a set of extracellular matrix markers that consists of TIMP-1, PIIINP, and HA, and has been reported to show good correlations with fibrosis stages in chronic liver disease (Lichtinghagen et al., 2013).

Total bile acids, C4, and FGF19 are biomarkers that will be utilized in this study to assess bile acid homeostasis. Factors implicated in the pathogenesis of NASH, such as obesity or increased BMI, insulin resistance, and elevated AST and ALT serum concentrations to the dysregulation and increase of serum bile acids. Likewise, elevations in serum C4, an indicator of bile acid synthesis in vivo, have been observed in NASH patients. Conversely, reduced serum concentrations of FGF19, which inhibits the rate-limiting enzyme CYP7A1 to regulate bile acid synthesis, have also been observed in NASH patients (Zhang and Deng 2018). Furthermore, the results of a recent study of BBR administered to wild type and farnesoid X receptor (FXR)

knockout mice suggest that BBR may exert its lipid-lowering effect by modulating bile acid turnover and activating the FXR-FGF19 signaling pathway (Sun et al., 2017).

6.3 SAFETY ASSESSMENTS

6.3.1 Physical Examinations

Physical examinations must be performed at investigational sites by medically qualified individuals according to local requirements. Abnormal physical examination findings that the Investigator considers clinically significant are to be reported as AEs.

The comprehensive physical examination will include the assessment of the following: skin; head, neck, eyes, ears, nose, throat; upper and lower extremities; chest and lungs; abdomen; cardiovascular system; and a brief neurological examination. The targeted physical examination will be a symptom-driven assessment of body systems or organs as indicated by AEs or other findings.

6.3.2 Vital Signs, Height, and Weight

Vital sign measurements must be performed at investigational sites by medically qualified individuals according to local requirements. Measurements include blood pressure, pulse, respiratory rate, and body temperature. Blood pressure and pulse will be taken in a recumbent, semirecumbent, or sitting position after 5 minutes of rest. Height (at Screening only) and weight will also be performed. Abnormal findings that the Investigator considers clinically significant are to be reported as AEs.

6.3.3 Electrocardiograms

Twelve-lead ECGs will be performed at the investigational site with the subject in a recumbent or semirecumbent position after 5 minutes of rest. Local institutional standards for QT interval corrections should be utilized. Interpretation of ECG results for the ongoing assessment of safety will be performed by the Investigator or qualified designee during the scheduled visit. Abnormal ECG readings that the Investigator considers clinically significant are to be reported as AEs. Additionally, the Investigator should consult the Medical Monitor, when possible, for any abnormal, clinically significant ECG findings that may result in a change to the subject's treatment or management.

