Name of sponsor company: HighTide BioPharma Pty. Ltd.

Name of finished product: HTD1801 Tablets

Name(s) of active ingredient(s): Berberine Ursodeoxycholate (HTD1801)

Analysis of Primary Endpoint:

The primary endpoint is absolute change from Baseline to Week 18 in LFC, or absolute change from Baseline to the Early Termination (ET) visit for subjects who terminate the study prematurely. Absolute change from Baseline in LFC will be assessed by analysis of covariance that includes the effects of treatment group, Baseline LFC, and Baseline ALT. Comparison of each active treatment group to placebo will be tested at the 5% level of significance without adjustment for multiple tests. Secondarily, comparison of the 2 active treatment groups with each other will be tested at the 5% level.

Analysis of Secondary Endpoints:

Relative (percent) change from Baseline in LFC will be analyzed by the same model described for the primary endpoint. Normalization of LFC will be analyzed by logistic regression that includes the effects of treatment group, Baseline LFC, and Baseline ALT.

All additional secondary endpoints are continuous and each will be assessed by analysis of covariance that includes treatment group and the Baseline value of the analysis variable. All secondary analyses (except LFC) will have missing Week 18 values imputed using a multiple imputation procedure for all subjects with an available measurement prior to Week 18.

Safety Evaluation

Safety Endpoints:

Adverse events and changes in physical examination, vital signs, electrocardiogram (ECG), and clinical laboratory values will be used to evaluate safety and tolerability. Adverse event incidence will be assessed during the Double-Blind Treatment Period. Adverse event type, relationship, severity, onset, and duration will be presented by treatment group within the Double-Blind Treatment Period.

Safety Analysis:

Changes in physical examination, vital signs, ECG, and clinical laboratory values will be presented using summary statistics. Numbers and percentages of the first occurrence for each adverse event will be presented.

Sample Size:

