| Height | 6.3.2 | X | | | | | | | | |
| ECG | 6.3.3 | X | Xa | | X | | X | X | X | |
| Laboratory Assessments | | | | | | | | | | |
| Serum chemistry panel ^c | 6.2.2, 6.3.4 | X | X | X | X | X | X | X | X | |
| Lipid panel ^c | 6.2.2, 6.3.4 | X | X | | | X | | X | X | |
| Hematology with differential ^c | 6.3.4 | X | X | | | X | | X | X | |
| Coagulation panel ^c | 6.3.4 | X | X | | | X | | X | X | |

Clinical Protocol

| | Protocol | | | | Double-Blin | d Treatment | | | | |
|-----------------------------------|--------------------|-----------|-----------------------|------|-------------|-------------|-------|-------|----|-----------|
| | Section(s) | SCR | Baseline | WK 2 | WK 6 | WK 10 | WK 14 | WK 18 | ET | Follow-up |
| Visit Day | | -28 to -1 | 0 | 14 | 42 | 70 | 98 | 126 | | +30d |
| Procedure / Window | - | - | - | ±3d | ±3d | ±3d | ±3d | ±3d | - | +7d |
| HbA1c | 6.2.2 | У | ζ ^d | | | X | | X | X | |
| HOMA-IR | 6.2.2 | | X | | | | | X | X | |
| HIV and Hepatitis B/C | 6.3.4 | X | | | | | | | | |
| G6PD | 6.3.4 | X | | | | | | | | |
| Pregnancy test ^e | 6.3.4 | X | X ^{a,e} | | | | | X | X | |
| FSH test ^e | 6.3.4 | X | | | | | | | | |
| Urine drug test | 6.3.4 | X | | | | | | | | |
| Imaging and Biomarker Assessmen | its | | | | | | | | | |
| MRI-PDFF | 6.2.1 | У | ζ^{d} | | | | | X | X | |
| Corrected T1 and T2* | 6.2.1 | У | ζ^{d} | | | | | | | |
| Pro-C3 | 6.2.2 | | X | | | | | X | X | |
| ELF test | 6.2.2 | | X | | | | | X | X | |
| Bile acid panel ^c | 6.2.2 | | X | | | X | | X | X | |
| Safety Assessments | | | | | | | | | | |
| Adverse event monitoring | 6.3.5, 7.0 | X | Xa | X | X | X | X | X | X | X |
| Prior and concomitant medications | 4.5, 4.6, 6.3.6 | X | Xª | X | X | X | X | X | X | X |

^a Continued study eligibility confirmed based on updated medical history, targeted physical examination, vital signs, weight, ECG, negative urine pregnancy test (for FOCP), updated prior and concomitant medications, and any adverse events that have occurred since signing informed consent.

ET = Early Termination; SCR = Screening

^b Targeted physical examination of body systems or organs performed on symptom-driven basis (e.g., adverse events or other findings).

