3.3 STUDY POPULATION

Approximately 117 patients with NASH and T2DM will be enrolled as subjects from approximately 15 investigational sites in the US. Eligibility will be established by the Investigator on the basis of the inclusion and exclusion criteria.

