9.2.5 Safety Analysis

The safety dataset will be used for all safety analyses. Safety analyses will address AEs, physical examinations, vital signs, ECGs, and clinical laboratory assessments.

Adverse event type will be coded using MedDRA. Adverse event data will be listed individually; AE incidence will be summarized by system organ class and preferred terms within a system organ class for each treatment group. Adverse event type, relationship, severity, onset, and duration will be presented by treatment group within the Double-Blind Treatment Period. Liver-specific AEs also will be included.

The number of subjects with AEs, as well as the number of AEs, also will be displayed. At the subject-level, each AE will be counted only once for a given subject within a specified system organ class, preferred term. If the same AE occurs on multiple occasions for a subject, the occurrence with the highest severity and relationship to study medication will be reported. Individual AE terms will be reported as separate events.

Changes in vital signs, ECGs, and clinical laboratory parameters from Baseline to end of study will be examined and displayed using shift tables (low, normal, high). Shift tables for Week 18, or the last available study visit, will be presented relative to Baseline for all clinical laboratory parameters.

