5.3.2. Clinical Laboratory Assessments, Vital Signs, Height, and Weight

Descriptive summaries of selected (quantitative) clinical laboratory results, and change from Baseline will be presented by time point and treatment group. Laboratory abnormalities will also be summarized by treatment group. Shift tables (low, normal, high) for change from Baseline to Week 18, or last available study visit, will be presented for all appropriate clinical laboratory parameters. Additionally, shift tables (normal, abnormal) for change from Baseline to Week 18, or last available study visit, will be presented for the clinical laboratory parameters listed below. Laboratory abnormalities will be determined using the following criteria:

Laboratory Parameter	Clinically Significant Abnormal Criteria
ALP	> 348 U/L
ALT	> 123 U/L
AST	> 102 U/L
Direct Bilirubin	> 0.20 mg/dL
Total Bilirubin	> 2.00 mg/dL

GGT	> 156 U/L in Males > 114 U/L in Females
Glucose	< 60 mg/dL
INR	≥ 1.3
HbA1c	≥ 9.5%

Additionally, descriptive summaries and change from Baseline in weight will be presented by timepoint and treatment group.

Values for all safety variables will be listed by subject and visit (as applicable).

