- 14.3.1.4 Treatment-Emergent Serious Adverse Events by System Organ Class and Preferred Term – Safety Set
- 14.3.1.5 Treatment-Emergent Adverse Events Leading to the Discontinuation of Study by System Organ Class and Preferred Term – Safety Set
- 14.3.4.1 Clinical Laboratory Chemistry Parameters by Time Point – Safety Set
- 14.3.4.2 Clinical Laboratory Hematology Parameters by Time Point – Safety Set
- 14.3.4.3 Clinical Laboratory Urinalysis Parameters by Time Point – Safety Set
- 14.3.4.4 Clinical Laboratory Abnormalities – Safety Set
- 14.3.4.5 Clinical Laboratory Parameter Shifts from Baseline to Week 18 – Safety Set
- 14.3.4.6 Clinical Laboratory Parameter Shifts to Abnormal from Baseline to Week 18 – Safety Set
- 14.3.5.1 Vital Signs by Study Visit – Safety Set
- 14.3.5.2 12-Lead ECG Assessments by Study Visit – Safety Set

Summary Figures

Efficacy

- 14.2.1.3 Bar Plot of Mean Absolute Change from Baseline at Week 18 in LFC
- 14.2.1.4 Bar Plot of Mean Percent Change from Baseline at Week 18 in LFC
- 14.2.1.5 Bar Plot of Proportion of Subjects with $\geq 30\%$ Reduction in LFC from Baseline to Week 18
- 14.2.1.6 Bar Plot of Proportion of Subjects who normalize LFC to $< 5\%$ at Week 18
- 14.2.1.7 Bar Plot of Proportion of Subjects who achieve $\geq 5\%$ absolute reduction in LFC from Baseline to Week 18
- 14.2.3.1 Bar Plot of Mean Change from Baseline by Time Point in Fasting Glucose
- 14.2.3.2 Bar Plot of Mean Change from Baseline by Time Point in HbA1c
- 14.2.3.3 Bar Plot of Mean Change from Baseline by Time Point in HOMA-IR
- 14.2.3.4 Bar Plot of Mean Change from Baseline by Time Point in AST
- 14.2.3.5 Bar Plot of Mean Change from Baseline by Time Point in ALT
- 14.2.3.6 Bar Plot of Proportion of Subjects who Normalize ALT at Week 18
- 14.2.3.7 Bar Plot of Mean Change from Baseline by Time Point in Lipids
- 14.2.3.8 Bar Plot of Mean Change from Baseline by Time Point in Pro-C3
- 14.2.3.9 Bar Plot of Mean Change from Baseline by Time Point in ELF
- 14.2.3.10 Bar Plot of Mean Change from Baseline by Time Point in Total Bile Acids
- 14.2.3.11 Bar Plot of Mean Change from Baseline by Time Point in C4
- 14.2.3.12 Bar Plot of Mean Change from Baseline by Time Point in FGF19

Data Listings

- 16.2.1.1 Subject Disposition
- 16.2.1.2 Informed Consent

- 16.2.2.1 Protocol Deviations/Violations
- 16.2.2.2 Inclusion/Exclusion Criteria
- 16.2.3 Reasons for Exclusion from Analysis Sets
- 16.2.4.1 Demographics
- 16.2.4.2 Medical History

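### QT correction is left to each site with no common formula for analysis, and the ECG and vital-sign shift tables promised in the protocol are missing from the SAP

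*Protocol*

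**What the plan says.** Change in ECG is one of the safety measures in Protocol 3.4.2. ECGs are scheduled at Screening, Baseline, Weeks 6, 14 and 18, and Early Termination (Protocol Table 1).

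- **Reading and correction.** Protocol 6.3.3 has ECGs read at the site: "Interpretation of ECG results for the ongoing assessment of safety will be performed by the Investigator or qualified designee during the scheduled visit". On QT it says "Local institutional standards for QT interval corrections should be utilized". No formula, QTc category or QTc threshold appears in either document, and no central ECG reading is described.
- **Sites.** Protocol 3.3: "Approximately 117 patients with NASH and T2DM will be enrolled as subjects from approximately 15 investigational sites in the US". Neither Protocol 3.5 nor SAP 3.2 mentions stratification by site.
- **Analysis in the protocol.** Protocol 9.2.5: "Changes in vital signs, ECGs, and clinical laboratory parameters from Baseline to end of study will be examined and displayed using shift tables", with low, normal and high as the categories. The synopsis is less specific: "Changes in physical examination, vital signs, ECG, and clinical laboratory values will be presented using summary statistics".
- **Analysis in the SAP.** SAP 5.3 contains no ECG text. In SAP 5.3.2, low/normal/high shift tables "will be presented for all appropriate clinical laboratory parameters", and a second set (normal/abnormal) covers a short list of laboratory tests. SAP 10 lists Table 14.3.5.2, "12-Lead ECG Assessments by Study Visit", and Listing 16.2.9 for ECG, and Table 14.3.5.1 for vital signs by visit. Its shift tables, 14.3.4.5 and 14.3.4.6, are both for laboratory parameters.
- **Declared changes.** SAP 7 anticipates no deviation from the planned analysis.

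**The concern.** There are two separate gaps, and they meet in the same outputs.

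First, QTc is not measured directly. It is QT adjusted for heart rate, and the result depends on the formula. If sites use different formulas, a by-arm, by-visit summary of QTc averages quantities that are not the same variable. The square-root (Bazett) correction also turns a change in heart rate into an apparent change in QTc.

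Second, the protocol commits to ECG and vital-sign shift tables that the SAP does not produce. Protocol 9.2.1 makes the SAP the place for detailed analyses and output specifications, so nothing else in these documents fills the gap.

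At stake is the precision and comparability of a named safety measure. Efficacy is not affected. The gaps compound: if ECG shift tables were added and their categories used QTc, identical tracings could be classed differently at different sites.

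**Working it through.** **1. Figure in the plan.** There is none to reproduce. The documents state no QTc value, heart rate or formula. The heart rates, QT values and formulas below are assumptions, shown over a range.

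**2. Formulas.** With RR = 60/HR in seconds:
- Bazett: QT / RR^(1/2)
- Fridericia: QT / RR^(1/3)
- Framingham: QT + 154 × (1 − RR)
- Hodges: QT + 1.75 × (HR − 60)

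Dividing the first by the second gives Bazett = Fridericia × (HR/60)^(1/6).

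**3. Same tracing, two formulas (Fridericia QTc fixed at 400 ms).**

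| HR (bpm) | Uncorrected QT (ms) | Bazett (ms) | Bazett minus Fridericia (ms) |
|---|---|---|---|
| 60 | 400.0 | 400.0 | 0.0 |
| 65 | 389.5 | 405.4 | 5.4 |
| 70 | 380.0 | 410.4 | 10.4 |
| 75 | 371.3 | 415.2 | 15.2 |
| 80 | 363.4 | 419.6 | 19.6 |
| 90 | 349.4 | 428.0 | 28.0 |

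If uncorrected QT is instead fixed at 360 to 400 ms, the gap over 70 to 90 bpm is 9.9 to 32.0 ms. At 50 bpm it reverses, to between −10.1 and −11.3 ms.

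**4. Other formula pairs.** At QT 380 ms and 80 bpm, Fridericia gives 418.2, Framingham 418.5, Hodges 415.0 and Bazett 438.8 ms. The three non-Bazett values lie within 3.5 ms of each other. Bazett is more than 20 ms above all of them. The size in step 3 therefore depends on at least some sites using Bazett.

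**5. Change from Baseline.** Suppose a site keeps one formula and heart rate does not change. The offset then almost cancels: at a constant 80 bpm, Bazett is 419.6/400 = 1.049 times Fridericia, so a 10 ms Fridericia change reads as 10.5 ms. If heart rate moves, it does not cancel. With Fridericia QTc constant at 400 ms and heart rate rising from 70 to 75 bpm, Bazett shows 415.2 − 410.4 = +4.8 ms and Fridericia shows 0. The 4.8 ms is a property of Bazett and would arise even if every site used it. Mixing formulas means that some sites show it and others do not.

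**6. Noise or bias.** Take the least favourable mix, with half the subjects at Bazett sites, and everyone at 80 bpm. The mix adds a standard deviation of 19.6 × √(0.5 × 0.5) = 9.8 ms to absolute QTc. With 39 per arm (Protocol 9.2.6), ignoring dropout and any balance by site, its contribution to a difference between two arm means has mean zero and standard error 9.8 × √(2/39) = 2.2 ms.

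**7. Shift tables side by side.**

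| Data | Protocol 9.2.5 | SAP 5.3.2 and SAP 10 |
|---|---|---|
| Laboratory | Shift tables | Shift tables 14.3.4.5 and 14.3.4.6 |
| Vital signs | Shift tables | By-visit Table 14.3.5.1 only |
| ECG | Shift tables | By-visit Table 14.3.5.2 only |

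This second gap needs no assumption.

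**The case against.** The case against has force on several points.

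- **Content of the table.** A reader might infer that Table 14.3.5.2 is a QTc table and pools mixed formulas. The documents do not say so: only the title is given, and the table could hold normal/abnormal readings. The correction sentence stands in a paragraph about investigator reading for ongoing safety. This stands, so the point covers any QTc summary and does not assert that one exists.
- **Size.** A reader might take 10 to 28 ms as the general error at ordinary heart rates. It is not. It needs 70 to 90 bpm and a Bazett/Fridericia mix. The gap is 0 at 60 bpm, and no document shows which formula any site uses.
- **Bias.** A reader might infer a distorted comparison between arms. Central, double-blind 1:1:1 randomisation makes any imbalance in formula mix a matter of chance, and the safety measure is change, in which a fixed offset largely cancels. This stands.
- **Safety question.** A reader might conclude that the trial cannot answer its ECG safety question. The documents pose no QT-specific question. Clinically significant ECG findings are reported as adverse events, a monitoring board oversees safety, and pulse is measured at the same visits and summarised in its own table.
- **Data capture.** The eCRF is not available here. QT and heart rate may already be collected.
- **Shift tables.** The synopsis promises only summary statistics, Protocol 9.2.1 leaves detail to the SAP, and SAP 7 is largely about later departures from the SAP. That makes an undeclared omission less serious, but it does not reconcile the SAP with Protocol 9.2.5.

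What remains is a stated rule with no common derivation behind it, and two sets of promised outputs that are absent.

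**Conclusion.** The point holds in a limited form. QT correction is site-specific and no common formula is named, so any QTc result summarised or classified across sites could mix formulas. The size in step 3 rests on a Fridericia QTc of 400 ms and a mix of Bazett and Fridericia sites, and would be a few milliseconds if no site uses Bazett. The consequence is noise in absolute values and a change from Baseline that depends on heart rate at some sites and not at others. The documents do not support a claim of systematic bias between arms.

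The missing ECG and vital-sign shift tables are a plain mismatch between Protocol 9.2.5 and the SAP and depend on no assumption. Both gaps are worth correcting because the correction is cheap. Neither touches the primary analysis.

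**What to change.** 1. Leave local ECG reading for patient care as it is.
2. Capture uncorrected QT and heart rate (or RR) for each ECG, if the eCRF does not already do so.
3. In the SAP, list the variables in Table 14.3.5.2 and derive QTc for all subjects with one prespecified formula, for example Fridericia. This sets the between-formula difference to zero by construction. Use the same derived value in any ECG category based on QTc.
4. Either add ECG and vital-sign shift tables, with the categories defined in the SAP, or state in SAP 7 that the tables in Protocol 9.2.5 are dropped, and why.

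The cost is slightly more data entry if the fields are not already there, one derived variable, and two more tables if they are added. No power, alpha or sample-size figure changes.
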